# 5.5.2 Treatment after Initial Evidence of Radiologic Disease Progression

Immunotherapeutic agents such as pembrolizumab may produce antitumor effects by potentiating endogenous cancer-specific immune responses. The response patterns seen with such an approach may extend beyond the typical time course of responses seen with chemotherapeutic agents, and may manifest as a clinical response after an initial increase in tumor burden or even the appearance of new lesions.

If radiologic imaging shows progression, tumor assessment should be repeated > 4 weeks later in order to confirm progression, and study treatment may be continued at the Investigator's discretion while awaiting radiologic confirmation of disease progression. For the subjects who continue on study therapy beyond progression, further progression is defined as an additional 10% increase in tumor burden from time of initial PD. This includes an increase in the sum of diameters of all target lesions and/ or the diameters of new measurable lesions compared to the time of initial PD. Study treatment should be discontinued permanently upon documentation of further progression. If repeat imaging shows a reduction in the tumor burden demonstrating CR, PR or SD compared to the initial scan, treatment with study treatment may be continued or resumed.

## 5.6 **Duration of Follow Up**

Participants will be followed for 3 years by phone after removal from study or until death, whichever occurs first. Survival status should be checked every 6 months during that time. Participants removed from study for unacceptable adverse events will be followed until resolution or stabilization of the adverse event. Date and cause of death should be provided for participants who become deceased within the 3-year interval following removal from the study. Should a participant become pregnant while on trial, the patient will be withdrawn from the study. However, the outcome of the pregnancy and the newborn's health, if the pregnancy is carried to term, will be monitored.

## 5.7 Criteria for Taking a Participant Off Study

Patients may voluntarily withdraw from the study treatment at any time for any reason, and without prejudice to further treatment. In addition, patients may be withdrawn by the Investigator if they do not feel the patient is deriving clinical benefit or because the patient is experiencing unacceptable toxicity, patient is lost to follow up, or patient is not compliant with study procedures.

Patients who withdraw or are removed from the study treatment will have an off-treatment visit within 7 days of the decision to discontinue study treatment. The final visit will occur at the time the participant discontinues study medication. Following the Final Visit, participants will be followed for disease progression (if reason for treatment discontinuation is other than

progression) and survival, and reassessment for toxicity will be performed up to 30 days after the last treatment dose. Participants will be followed for up to 3 years by phone after removal from study or until death, whichever occurs first. Survival status should be checked every 6 months during that time

The reason for taking a participant off study, and the date the participant was removed, must be documented in the case report form (CRF). In addition, the study team will ensure Off Treatment/Off Study information is updated in OnCore in accordance with DF/HCC policy REGIST-101.

#### DOSING DELAYS/DOSE MODIFICATIONS

Every effort should be made to administer study treatment on the planned dose and schedule.

Dose delays and modifications will be made as indicated in the following table(s). The descriptions and grading scales found in the revised NCI Common Terminology Criteria for Adverse Events (CTCAE) version 5.0 will be utilized for dose delays and dose modifications. A copy of the CTCAE version 5.0 can be downloaded from the CTEP website http://ctep.cancer.gov/protocolDevelopment/electronic\_applications/ctc.htm.

Patients experiencing AEs that can be clearly attributed to mirvetuximab soravtansine or pembrolizumab will have the corresponding agent modified or withheld. In case of an AE recurrence, the other drug in the combination regimen will then be modified or withheld. If a relationship of an AE to a particular drug cannot be clearly determined, the order in which the drugs are to be reduced will require approval from the Overall PI.

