If a patient develops ocular symptoms of any grade, the patient is required to have a complete examination by an ophthalmologist. If a patient develops  $\geq$  CTCAE Grade 2 ocular symptoms, treatment with mirvetuximab soravtansine will be interrupted. Therapy may resume if ocular symptoms improve to Grade 1 or baseline within 28 days of the next scheduled mirvetuximab soravtansine dose (refer to Table 3 for details). Subsequent eye examinations will be scheduled to occur in every other cycle going forward, from the time that the AE was initially reported, and at either the End of Treatment visit or 30-day follow-up visit following treatment discontinuation, even if the results of the patient's ocular exam shows no obvious clinical findings. Management of treatment-emergent ocular AEs with inflammatory characteristics should include corticosteroid eye drops and/or other measures as indicated by an ophthalmologist.

CTCAE v5.0 Severity Grade*	Management	Guidelines for Mirvetuximab Soravtansine Dose Modifications
Grade 1	
 
Complete eye exam as outlined in Study Calendar and Appendix C.
 
Monitor for worsening symptoms
 
Repeat complete exam as clinically indicated, at least every other cycle (from point at which toxicity first reported) at a minimum
 
	Continue mirvetuximab soravtansine dosing
Grade 2	
 
Complete eye exam as outlined in schedule of clinical assessments (Study Calendar and Appendix C).
 
Repeat complete exam as clinically indicated
 
Patients should have weekly symptomatic ocular assessments until the symptoms resolve to Grade 1 or baseline or are deemed to irreversible by investigator
 
Repeat complete exam as clinically indicated, at least every other cycle (from point at which toxicity first reported) at a minimum
 
	
 
Hold mirvetuximab soravtansine dosing until AE has resolved to Grade 1 or better.
 
Patients with ocular symptoms lasting < 14 days may be allowed to resume mirvetuximab soravtansine at the same dose level
 
Patients with ocular symptoms lasting ≥ 14 days but no more than 28 days may resume mirvetuximab soravtansine reduced by one dose level
 

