# Table 3: Management of Ocular Disorders

	Tototot Version Bute. December 11, 2025				
Grade 3	
 
Complete eye exam as outlined in schedule of assessments (Study Calendar and Appendix C). Repeat complete exam as clinically indicated.
 
Patients should have weekly symptomatic ocular assessments until the symptoms resolve to Grade 1 or baseline or are deemed to be irreversible by the investigator.
 
Repeat complete exam as clinically indicated, at least every other cycle (from point at which toxicity first reported) at a minimum
 
	
 
Hold mirvetuximab soravtansine dosing.
 
Patients may be allowed to resume mirvetuximab soravtansine reduced by one dose level after AE has resolved to Grade 1 or better within 28 days.
 
			
Grade 4	
 
Complete eye exam as outlined in Study Calendar and Appendix C Repeat complete exam as clinically indicated.
 
Patients should have weekly symptomatic ocular assessments until the symptoms resolve to Grade 1 or baseline (Study Calendar and Appendix C) or are deemed to be irreversible by the investigator.
 
Repeat complete exam as clinically indicated, at least every other cycle (from point at which toxicity first reported) at a minimum
 
	Permanently discontinue mirvetuximab soravtansine dosing.			
* Appendix C includes CTCAE version 5.0 Grade definitions for select ocular disorders					

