### **Table 6: Mirvetuximab Soravtansine Dose Levels**

Dose Level	Mirvetuximab Soravtansine Dose
-2	4 mg/kg AIBW, Q21 day
-1	5 mg/kg AIBW, Q21 day
0	6 mg/kg AIBW, Q21 day

A second dose reduction will be permitted for second event of Grade 3 or higher. Dose reductions below 4 mg/kg (Dose Level -2) will not be permitted.

Mirvetuximab soravtansine may be interrupted for situations other than treatment-related Aes such as medical / surgical events or logistical reasons not related to study therapy. Participants should be placed back on study therapy within 3 weeks of the scheduled interruption, unless otherwise discussed with the Overall PI. The reason for interruption should be documented in the patient's study record.

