### **Restarting Study Interventions:**

Participants may not have any dose modifications (no change in dose or schedule) of pembrolizumab in this study, as described in Table 7.

- If the toxicity does not resolve or the criteria for resuming treatment are not met, the participant must be discontinued from all study interventions.
- If the toxicities do not resolve and conditions are aligned with what is defined in Table 7, the combination of mirvetuximab soravtansine and pembrolizumab bay be restarted at the discretion of the investigator. In these cases where the toxicity if attributed to the combination or to mirvetuximab soravtansine alone, re-initiation of pembrolizumab as a monotherapy may be considered at the PI's discretion.

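### When an adverse event attributed to one agent recurs, Section 6 acts on the other drug, while Table 3, the note under Table 6 and Section 6.3 act on the attributed one

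*Combined protocol and SAP*

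**What the plan says.** The introduction to Section 6 (Dosing Delays/Dose Modifications) refers the reader to the tables that follow and then sets two general rules. For an event of clear attribution: "Patients experiencing AEs that can be clearly attributed to mirvetuximab soravtansine or pembrolizumab will have the corresponding agent modified or withheld". For a repeat: "In case of an AE recurrence, the other drug in the combination regimen will then be modified or withheld". A third sentence covers events whose attribution is unclear and sends the order of reduction to the Overall PI.

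For ocular events, Section 6.1.1 says that at Grade 2 or higher "treatment with mirvetuximab soravtansine will be interrupted". In Table 3, patients with a Grade 2 event lasting 14 to 28 days "may resume mirvetuximab soravtansine reduced by one dose level". The Grade 3 row holds mirvetuximab and then gives this option: "resume mirvetuximab soravtansine reduced by one dose level after AE has resolved to Grade 1 or better within 28 days". An event of Grade 4 ends mirvetuximab permanently. None of these entries mentions pembrolizumab.

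Table 6 lists mirvetuximab levels of 6, 5 and 4 mg/kg, and the note beneath it adds: "A second dose reduction will be permitted for second event of Grade 3 or higher".

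On pembrolizumab, Section 6.2 states: "Participants may not have any dose modifications (no change in dose or schedule) of pembrolizumab in this study, as described in Table 7". The Table 7 instructions and the closing note of Section 6.2 nevertheless allow it to be withheld or interrupted and later resumed.

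Section 6.3 says that where an event can be attributed to one agent, that agent is held or discontinued under Section 6.1 or 6.2, and the second agent may resume if the other criteria are met.

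**The concern.** The recurrence sentence is mandatory, has no exception for ocular events, and names a different drug from the one named in the ocular rules and in Section 6.3. An investigator facing a repeat event can follow one part of Section 6 and depart from another.

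Recurrence is foreseeable. Section 6.1.1 reports that the likelihood of ocular events rose with mirvetuximab exposure in early dose escalation, and ocular symptoms are assessed on Day 1 of every cycle. At stake is consistent handling across sites of a recurrent toxicity that the protocol itself singles out for monitoring. Also at stake is consistent delivery of the two-drug combination in a trial of at most 35 patients.

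**Working it through.** No figure in the plan bears on this, so the check is to trace one case through each rule.

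**Case.** A patient starts at 6 mg/kg, has a first Grade 3 ocular event attributed to mirvetuximab, and resumes at 5 mg/kg. A second Grade 3 ocular event follows, again attributed to mirvetuximab and not judged immune-related.

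| Rule | Mirvetuximab | Pembrolizumab |
|---|---|---|
| Section 6, recurrence sentence | no further action stated | modified or withheld |
| Section 6.1.1 and Table 3, Grade 3 | held; may resume one level lower if resolved to Grade 1 or better within 28 days | no action stated |
| Note under Table 6 | second reduction permitted | not addressed |
| Section 6.2 and Table 7 | no ocular row | no dose or schedule change; withholding possible in general |
| Section 6.3 | held or discontinued, as the attributed agent | may resume if other criteria are met |

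**Size of the step in this case.** From level -1 to level -2: (5 − 4)/5 = 20% less mirvetuximab under Table 3 and the Table 6 note. The recurrence sentence states no mirvetuximab change and acts on pembrolizumab.

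**The word *modified*.** The recurrence sentence offers two actions on the other drug. When that drug is pembrolizumab, Section 6.2 excludes modification in the sense of a changed dose or schedule. Withholding remains possible. Section 6.2 therefore removes one of the two options and does not make the sentence unworkable.

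**How far the case generalises.** Table 3 has no row for recurrence. A further reduction follows from applying its grade rules again together with the Table 6 note, so the repeat Grade 3 event is the clearest example. At other grades:

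- A Grade 2 ocular event lasting under 14 days may resume at the same level, so a repeat need not bring a reduction.
- A Grade 4 ocular event ends mirvetuximab.

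Some recurrent events have rules of their own:

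- Recurrent Grade 2 pneumonitis stops both agents (Table 4).
- Recurrent Grade 3 events among the other immune-related events stop pembrolizumab (Table 7).
- A Grade 2 pembrolizumab infusion reaction despite premedication ends study drug treatment (Table 2).

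**The case against.** The strongest reply is that the tables govern. Section 6 opens by saying that modifications follow the tables, Section 6.1.1 gives specific ocular instructions naming mirvetuximab, and Section 6.3 refers attributed events back to Sections 6.1 and 6.2. A careful investigator would probably go to Table 3. This has weight, but the recurrence rule is a separate, unqualified instruction placed after the pointer to the tables, and nothing says which prevails.

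A second reply is that the other drug is acted on in addition to the attributed one. The sentence on attributed events is not limited to first occurrences, and the recurrence sentence does not say *instead*. That reading is open, though the text does not state it. It does not remove the conflict: pembrolizumab would have to be modified or withheld for an ocular event for which Table 3 gives no pembrolizumab action and Section 6.3 allows it to resume.

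Several stronger readings are tempting and are not supported:

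- That Section 6 leaves mirvetuximab at its current dose after a repeat event. It only states no further action on it.
- That Section 6.2 forbids any action on pembrolizumab. It bars a change of dose or schedule; withholding and interruption are allowed.
- That the phrase on the order in which drugs are reduced adds to the conflict. It belongs to the sentence on unclear attribution.
- That Tables 3 and 6 require a further reduction after every repeat ocular event. The second reduction is permitted rather than required, and the Grade 2 and Grade 4 rules differ.
- That every recurrent attributed event outside Table 7 is affected. Tables 2 and 4 show otherwise.

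**Conclusion.** The point holds as an internal contradiction over which drug is acted on when an event attributed to one agent recurs. It is clearest for a second Grade 3 ocular event attributed to mirvetuximab, where the recurrence sentence points to pembrolizumab and Table 3, the Table 6 note and Section 6.3 point to mirvetuximab. The conflict survives whether the recurrence sentence is read as replacing the action on the attributed drug or as adding to it.

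In the traced case the difference is a permitted 20% mirvetuximab reduction with no stated pembrolizumab action, against an action on pembrolizumab with no further mirvetuximab action stated. This assumes that the first event led to the one-level reduction and that the second was judged not immune-related. The documents give no frequency of repeat events, so the number of patients affected cannot be estimated.

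The trial's hypotheses, decision rules and sample size are untouched. The point should be corrected because mandatory safety instructions conflict and the correction is cheap. No view is taken on which rule is clinically right.

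**What to change.** Reconcile the recurrence sentence in the introduction to Section 6 with Section 6.1.1 and Table 3, Tables 5 and 6, Section 6.2 and Section 6.3. One consistent instruction should state:

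1. which agent or agents are acted on when an attributed event recurs, and whether any action on the second agent replaces or adds to action on the first;
2. whether the event-specific tables take precedence over the general rule;
3. what *modified* means for pembrolizumab, given the bar in Section 6.2 on dose and schedule changes.

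Which clinical rule stands is for the sponsor to decide. The cost is about two sentences in the Section 6 introduction, with matching edits elsewhere only if the sponsor's choice requires them. No change to the design, the sample size or the analysis is needed.

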### 6.1 Mirvetuximab Soravtansine (IMGN853)

## 6.1.1 Monitoring and Management of Potential Ocular Disorders

In early dose escalation, there was a relationship between mirvetuximab soravtansine plasma exposure with increased likelihood of an ocular event as well as with response. Exposure-response modeling suggested that a dose of 6.0 mg/kg AIBW provided adequate exposure for response while also maintaining overall exposure within a range that decreased the potential for ocular adverse events. Due to the observation of ocular disorders consistent with reversible keratopathy/corneal epitheliopathy in patients treated with mirvetuximab soravtansine, ocular function will be carefully monitored. Ocular symptom assessments will be performed at baseline and at Day 1 of every cycle thereafter (Study Calendar and Appendix C). Complete ophthalmologic exams will be performed in all patients at baseline and every other cycle thereafter if there is a TEAE reported (Study Calendar and Appendix C).

Patients are strongly advised to avoid using contact lenses while on mirvetuximab soravtansine. Baby shampoo and a soft cloth should be used to clean the eyes, and a warm compress at bedtime may be used to decrease any possible inflammation on the eyelid's surface. Please refer

to Section 5.4 for details on the prophylactic use of steroid eye drops and lubricating artificial tears. The use of UVA/UVB sunglasses is recommended in full daylight during the course of the study. The use of temporary lower punctal plugs to increase lubrication of the eyes is optional if lubricating artificial tears and corticosteroid eye drops are not sufficient. If patients report signs or symptoms of ocular disorders, including, but not limited to, blurred vision or eye irritation, the management and dose modification is outlined below.

If a patient develops ocular symptoms of any grade, the patient is required to have a complete examination by an ophthalmologist. If a patient develops  $\geq$  CTCAE Grade 2 ocular symptoms, treatment with mirvetuximab soravtansine will be interrupted. Therapy may resume if ocular symptoms improve to Grade 1 or baseline within 28 days of the next scheduled mirvetuximab soravtansine dose (refer to Table 3 for details). Subsequent eye examinations will be scheduled to occur in every other cycle going forward, from the time that the AE was initially reported, and at either the End of Treatment visit or 30-day follow-up visit following treatment discontinuation, even if the results of the patient's ocular exam shows no obvious clinical findings. Management of treatment-emergent ocular AEs with inflammatory characteristics should include corticosteroid eye drops and/or other measures as indicated by an ophthalmologist.

CTCAE v5.0 Severity Grade*	Management	Guidelines for Mirvetuximab Soravtansine Dose Modifications
Grade 1	
 
Complete eye exam as outlined in Study Calendar and Appendix C.
 
Monitor for worsening symptoms
 
Repeat complete exam as clinically indicated, at least every other cycle (from point at which toxicity first reported) at a minimum
 
	Continue mirvetuximab soravtansine dosing
Grade 2	
 
Complete eye exam as outlined in schedule of clinical assessments (Study Calendar and Appendix C).
 
Repeat complete exam as clinically indicated
 
Patients should have weekly symptomatic ocular assessments until the symptoms resolve to Grade 1 or baseline or are deemed to irreversible by investigator
 
Repeat complete exam as clinically indicated, at least every other cycle (from point at which toxicity first reported) at a minimum
 
	
 
Hold mirvetuximab soravtansine dosing until AE has resolved to Grade 1 or better.
 
Patients with ocular symptoms lasting < 14 days may be allowed to resume mirvetuximab soravtansine at the same dose level
 
Patients with ocular symptoms lasting ≥ 14 days but no more than 28 days may resume mirvetuximab soravtansine reduced by one dose level
 

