### 5.3 Agent Administration

## 5.3.1 Mirvetuximab Soravtansine (IMGN853)

Dosing

Mirvetuximab soravtansine 6 mg/kg by Adjusted Ideal Body Weight (AIBW) IV on Day 1 of each 21-day cycle. Dosing by AIBW as follows:

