#### 6.3 **Re-treatment Criteria**

For a patient to begin a new cycle or continue a cycle of therapy after a dose modification, the following criteria must be met.

- Pre-treatment criteria as described in Section 5.2.2 with the following exceptions
  - $\circ$  Treatment-emergent ocular disorders, which must have recovered to  $\leq$  Grade 1 or baseline
  - $\circ$  Treatment-emergent pneumonitis which must have recovered to  $\leq$  Grade 1

If the patient does not meet these criteria, dosing with the two agents in the combination regimen will be delayed and the patient should be re-evaluated within 48-72 hours. Dosing with both agents may resume if these criteria have been met. If the adverse event can be attributed to one of the agents in the combination regimen, that agent will be held or discontinued as per the Dose Modification Guidelines

described in Sections 6.1 and 6.2 respectively; however, treatment with the second agent may resume provided all the other criteria are met. However, if the next cycle is delayed due to treatment-related toxicity longer than 12 weeks then the patient should be removed from study treatment. In such cases, continuation of study treatment may be considered for those patients who have experienced clinical benefit if agreed upon between the Overall PI and the Investigator.

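### For Grade 2 ocular events, the 28-day limit on resuming mirvetuximab runs from the next scheduled dose in the Section 6.1.1 text but is a limit on symptom duration in Table 3, and the table has no provision beyond it

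*Combined protocol and SAP*

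**What the plan says.** The text of Section 6.1.1 interrupts mirvetuximab for ocular symptoms of Grade 2 or higher. It then states: "Therapy may resume if ocular symptoms improve to Grade 1 or baseline within 28 days of the next scheduled mirvetuximab soravtansine dose". The same sentence refers the reader to Table 3 for details.

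Table 3 gives rules by grade:

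- **Grade 2, dose column.** The first bullet reads "Hold mirvetuximab soravtansine dosing until AE has resolved to Grade 1 or better" and has no time limit. The second allows the same dose level if symptoms lasted under 14 days. The third reads "Patients with ocular symptoms lasting ≥ 14 days but no more than 28 days may resume mirvetuximab soravtansine reduced by one dose level". Nothing covers longer durations.
- **Grade 3, dose column.** Mirvetuximab may be resumed "reduced by one dose level after AE has resolved to Grade 1 or better within 28 days". The row does not say when the 28 days begin.
- **Grade 4.** Permanent discontinuation. This is the only row that orders it.

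The recovery target is Grade 1 or baseline in the Section 6.1.1 text, in Section 6.3 and in the management column of the Grade 2 and Grade 3 rows. In the dose column of those rows it is Grade 1 or better.

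Three other places bear on the point. Section 5.3.1 gives mirvetuximab "IV on Day 1 of each 21-day cycle". The opening of Section 6 says that delays and modifications follow the tables. Section 6.3 sets a general backstop: "if the next cycle is delayed due to treatment-related toxicity longer than 12 weeks then the patient should be removed from study treatment". It allows an exception by agreement for patients with clinical benefit.

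**The concern.** The same decision, whether a patient with a Grade 2 ocular event may receive mirvetuximab again and at what dose level, is governed by two limits. They share the number 28 but count different things. One counts days after a scheduled dosing date; the other counts days of symptoms. They agree only when symptoms begin on the date the next dose is due.

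At stake is consistent re-dosing after eye toxicity. Section 2.2 lists blurred vision, dry eye, keratopathy and reduced visual acuity among the common adverse events of this drug, so the rule will probably be used. Two sites could handle the same course of symptoms differently, each with support in the protocol, and a monitor would have no firm basis for calling either one a deviation.

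**Working it through.** The plan states no figure to reproduce. The check is timeline arithmetic followed by a comparison of wording.

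**Inputs**

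- Cycle length: 21 days, so the next dose is due on day 22 counted from Day 1 of the current cycle (Sections 5.1 and 5.3.1).
- Section 6.1.1 text: improvement within 28 days of the next scheduled dose.
- Table 3, Grade 2 row: symptoms lasting no more than 28 days.

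**Formulas.** Let *d* be the cycle day on which symptoms begin.

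- Days from onset to the next scheduled dose: 22 − *d*.
- Longest symptom duration under the Section 6.1.1 text: (22 − *d*) + 28.
- Longest symptom duration provided for in the Grade 2 row: 28, whatever *d* is.
- Difference: 22 − *d*.

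| Onset day *d* | Days to next dose | Limit in 6.1.1 text (days of symptoms) | Limit in Table 3, Grade 2 | Difference |
|---|---|---|---|---|
| 1 (after dosing) | 21 | 21 + 28 = 49 | 28 | 21 |
| 8 | 14 | 14 + 28 = 42 | 28 | 14 |
| 15 | 7 | 7 + 28 = 35 | 28 | 7 |
| 21 | 1 | 1 + 28 = 29 | 28 | 1 |
| 22 (next dosing day) | 0 | 0 + 28 = 28 | 28 | 0 |

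**One patient through both rules.** Grade 2 blurred vision begins on cycle day 8 and reaches Grade 1 after 35 days. The next dose was due 14 days after onset, so improvement came 35 − 14 = 21 days after the scheduled dose. Since 21 ≤ 28, the text permits resumption. Symptoms lasted 35 days, and 35 > 28, so neither duration bullet in the Grade 2 row applies and the table supplies no dose level.

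**Hold and symptom duration are different lengths.** Nothing is withheld until the next dose falls due. In the example, symptoms last 35 days but the dose is late by only 21 at the point of improvement. The range in dispute is therefore one of symptom duration.

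**Grade 3.** The row's 28 days could run from onset, from the start of the hold or from the scheduled dose. Under the last reading it agrees with the Section 6.1.1 text, so no contradiction can be demonstrated, only a missing starting point.

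**Recovery target.** Grade 1 or baseline and Grade 1 or better give different answers only for a patient whose baseline is worse than Grade 1. Exclusion 3.2.8 removes active or chronic corneal disorders and several other eye conditions, so such patients should be uncommon.

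**The case against.** The strongest reply is that the protocol already says which rule operates. Section 6 opens by sending delays and modifications to the tables, and the Section 6.1.1 sentence itself points to Table 3. A site has good reason to treat the table as the rule and the sentence as a summary. This stands as far as it goes: it makes divergent practice less likely. It does not make the two consistent. If the table governs, the sentence states a wrong limit. If the sentence is the outer limit and the table only sets the dose, a patient between the two limits may resume with no dose level assigned. On either view the Grade 2 row has no action beyond 28 days.

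The 12-week limit in Section 6.3 does not settle it either. All the durations above are shorter than 12 weeks, and for an event attributed to one agent that section sends the reader back to Section 6.1 for mirvetuximab.

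Four stronger readings may tempt a reader, and the documents do not support them:

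- *Table 3 forbids resumption after 28 days at Grade 2.* It is silent. A bar is implied by the upper limit in the third bullet, but the hold-until-Grade-1 bullet has no time limit, and only the Grade 4 row orders permanent discontinuation.
- *The conflict covers all of Table 3.* The symptom-duration count is explicit only in the Grade 2 row.
- *Every hold of 29 to 49 days is in dispute.* The figures describe symptom duration, and 49 days is reached only when symptoms begin on the dosing day just after the dose.
- *ORR and PFS6 will be distorted.* Section 6.1.1 reports that exposure was related both to ocular events and to response, so an effect is conceivable. The documents give no frequency of ocular events in the disputed range, and no effect on either endpoint is shown.

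It is also fair to say that both rules require recovery to about Grade 1 before re-dosing. Apart from a patient whose baseline is worse than Grade 1, neither allows a dose while Grade 2 toxicity persists.

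**Conclusion.** The point holds for Grade 2 events. The Section 6.1.1 text and the Grade 2 row set different limits, 1 to 21 days apart for onset on cycle days 21 to 1 (42 against 28 days of symptoms for Day 8 onset). A patient between them may resume under one and has neither a provision nor a dose level under the other. At Grade 3 the finding is an ambiguity. The difference in recovery target is a minor wording inconsistency, present within Table 3 itself.

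The arithmetic assumes that the next scheduled dose is Day 1 of the following 21-day cycle, that the 28 days run forward from that date, and that onset is the day symptoms begin, not the visit at which they are recorded. Moving the dose date within the three-day administrative window would shift the text's limit by up to 3 days. The number of patients affected cannot be estimated from the documents. The correction is worth making because the rule governs re-dosing after eye toxicity and the change is one of wording only.

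**What to change.** Reconcile the Section 6.1.1 text, the Grade 2 and Grade 3 rows of Table 3, and the ocular item in Section 6.3, so that all of them use:

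1. one stated starting point for the 28-day limit, and for the 14-day cut-off that sets the dose level;
2. one recovery target, in the same words throughout, including both columns of Table 3;
3. a stated action once the limit has passed, with its relation to the 12-week rule in Section 6.3 made clear.

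Which of the existing rules stands is for the sponsor and clinical team to decide; this review takes no position on it.

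The cost is amendment wording in one paragraph and a few table cells, with a matching check of Section 6.3. Sample size, endpoints and assessment schedule are unaffected.
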